2.2.2 Secondary Endpoints

- 6 Month maintenance treatment completion as defined as completion of at least 2 of 3 maintenance treatments within a 5-week period without unacceptable toxicities or disease progression. Disease status will be evaluated based on cystoscopy and urine cytology prior to maintenance therapy.

Patients with persistent or recurrent high-grade disease at 6 Month cystoscopy will be taken off treatment. Low-grade recurrence will be tolerated without treatment interruption.

- 3-month and 6-month complete response (CR) based on negative cystoscopy and urine cytology.
- Recurrence free survival (RFS) at 6 and 12 months, defined as proportion of patients who are alive and free of persistent or recurrent NMIBC based on cystoscopy, cytology and/or biopsy.
- Progression-free survival (PFS) at 6 and 12 months, as defined by time from day of first treatment to first progression to higher grade or stage, including muscle-invasive disease or death from any cause
- Cystectomy-free survival (CFS), defined as time from study initiation to cystectomy or death
- Overall survival, defined as time from day of first treatment to death from any cause

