8.2 Efficacy Evaluation

Cystoscopy and urine cytology will be obtained at screening and at Month 3, 6, 9, and 12. Only frankly malignant cytology will be considered positive and used to determine the need for bladder biopsy and further evaluation. Three-month complete response (CR) rate, 6-month CR rate, recurrence free survival (RFS), cystectomy-free survival (C

FS), and overall survival will be evaluated as the following.

Time to High-Grade Recurrence (TTHGR) is defined as time from date of first treatment to first high-grade recurrence. Patients without a recurrence will be censored at their last cystoscopy date. Those who die without a recurrence are also counted as a recurrence and high-grade recurrence at time of death.

Time to Recurrence (TTR) is identical to TTHGR with the addition that failure with any-grade bladder cancer is considered an event.

Progression-free survival (PFS) is defined as time from date of first treatment to first evidence of muscle invasive bladder cancer, metastatic disease, or death due to any cause. Those without an event are censored at their last valid tumor assessment, or at the last tumor assessment before patient start of the new therapy if a patient has started new anti-cancer therapy.

Complete Response: For the subset of patients with CIS (with or without concomitant Ta or T1 disease) at study entry, a 6-month biopsy is required. A negative biopsy at 6 months will provide evidence of complete response. A +/- 10 day window will be allowed around the disease assessment time point. Patients receiving a second induction will not be required to undergo 6-month biopsy

Duration of Complete Response: For the subset of patients with CIS (with or without concomitant Ta or T1 disease) at study entry who achieve a CR, duration is defined as time from first documentation of CR to time of first high grade recurrence. Patients who remain CR at end of study (EOS) are censored at their last cystoscopy date.

Overall survival (OS) is defined as the duration from the first dose date of the study drug until death due to any cause. Patients who are still alive at EOS are censored on the date they will be last known to be alive. An exploratory analysis to determine OS at EOS will be estimated by the Kaplan-Meier method.

Patient Reported Outcomes:

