2. Endpoints

a. Primary Endpoint

- i. Completion of induction therapy with combined BCG + avelumab as defined as freedom from dose-limiting toxicity (DLT) (Section 5.2.1) preventing completion of at least 5 of 6 treatments of BCG + avelumab within 8 weeks.

b. Secondary Endpoint

- i. 6 Month maintenance treatment completion as defined as completion of at least 2 of 3 maintenance treatments within a 5 week period without DLT or disease progression. Disease status will be evaluated based on cystoscopy and urine cytology prior to maintenance therapy. Patients with persistent or recurrent high-grade disease at 6 Month cystoscopy will be taken off treatment. Low-grade recurrence will be tolerated without treatment interruption.
- ii. 3-month and 6-month complete response (CR) based on negative cystoscopy and urine cytology.
- iii. Recurrence free survival (RFS) at 6 and 12 months, defined as proportion of patients who are alive and free of persistent or recurrent NMIBC based on cystoscopy, cytology and/or biopsy.
- iv. Progression-free survival (PFS) at 6 and 12 months, as defined by time from day of first treatment to first progression to higher grade or stage, including muscle-invasive disease or death from any cause
- v. Cystectomy-free survival (CFS), defined as time from study initiation to cystectomy or death
- vi. Overall survival, defined as time from day of first treatment to death from any cause

c. Exploratory Endpoint

- i. To obtain preliminary data of potential biomarkers that would associate with tumor response from the combination of avelumab and intravesical BCG.
- ii. Avelumab combined with intravesical BCG will improve quality of life in patients with NMIBC.

3. Design information

a. General statistical considerations

- i. This is a single arm, phase Ib study. A total of 18 evaluable patients will be enrolled at the Stephenson Cancer Center. More than 40 patients with bladder cancer initiate intravesical BCG treatment in our Urologic Oncology clinic each year, including approximately 40% patients with BCG-treated but unresponsive NMIBC (persistent or recurrent) who are hopefully eligible for the proposed study. Based on our prior experience with a similar patient population, we anticipate enrollment of 1 patient per month.

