- xxvii. Administration of a live/attenuated vaccine within 4 weeks prior to the first dose of study treatment, within 5 months following the administration of the last dose of study drug, or anticipation that such a live/attenuated vaccine will be required during the study.
- xxviii. Other severe acute or chronic medical conditions including immune colitis, inflammatory bowel disease, immune pneumonitis, pulmonary fibrosis or psychiatric conditions including recent (within the past year) or active suicidal ideation or behavior; or laboratory abnormalities that may increase the risk associated with study participation or study treatment administration or may interfere with the interpretation of study results and, in the judgment of the investigator, would make the patient inappropriate for entry into this study.

5. Analysis Populations

The analysis populations are defined as below.

- a. **Safety population:** All patients who receive at least one dose of combination avelumab and BCG will be included in the analyses of compliance and safety.
- b. **Biomarker population:** For biomarker analysis, the biomarker population will comprise all evaluable patients who have sufficient baseline and on-study biomarker measurements.
- c. **Evaluable population:** Evaluable patients will be defined as patients who receive at least 5 doses of intravesical BCG and avelumab IV weekly during induction treatment and complete the first post-treatment cystoscopy and/or urine cytology for tumor assessment. Patients

who discontinued study treatment due to toxicity incurred by previous therapy will be evaluated for safety analysis, but will be replaced by additional patients for the efficacy analysis.

Patients removed from study for early withdrawal or hypersensitivity reactions will be replaced if they have received less than 5 doses of study treatment during induction treatment, but will be included in the safety analysis.

Patients who do not receive at least 5 doses of intravesical BCG and avelumab IV during induction treatment will be considered unevaluable for efficacy analysis and will be replaced unless the missed doses were due to development of grade 3-4 adverse events related to study treatment.

Evaluable population will be used for the analysis of EORTC QOQ-C30 (Section 6) and antitumor measures (Section 8).

6. Patient Population Summary

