5. The following may be considered as exceptions to DLTs: 1.
- a. Grade 3 nausea, vomiting, or diarrhea and Grade 4 vomiting or diarrhea in the absence of maximal medical therapy that resolves in 72 hours.
 - b. Grade 3 fatigue lasting < 5 days.
 - c. Grade 3 hypertension that can be controlled with medical therapy.
 - d. An increase of indirect (unconjugated) bilirubin indicative of Gilbert's syndrome.
 - e. Serum lipase and/or serum amylase CTCAE Grade 3 ≤ 7 consecutive days without clinical signs or symptoms of pancreatitis.

ii. **Definition of DLT Evaluable Population**

1. Patients enrolled in safety lead-in cohort who receive at least 4 doses and complete the DLT observation period (the first 42 days of induction treatment), unless the patient discontinued the study treatment due to a DLT.

8. Antitumor Evaluation

- a. The proportion of patients receiving a complete induction course (at least 5 of 6 treatments of BCG + avelumab within eight weeks of starting treatment) at 3 months and at 6 months will be calculated and a 95% Wilson score confidence interval constructed for the completion rate.
- b. The 3-month and/or 6-month complete response (CR) rates will be summarized as the proportion (and 95% CI) of patients with complete tumor response at month 3 or 6 of study treatment. Patients who remain CR at end of study (EOS) are censored at their last cystoscopy date.
- c. The duration of response will be calculated as time from the date of first response (complete response (CR), partial response (PR), pathological complete response (pCR)) to the first date of non-response. Duration of response will be summarized using the Kaplan-Meier method. Median duration of response with 95% CI will be computed. Results will be presented in tabular and graphic form, as appropriate.
- d. Progression-Free Survival (PFS) at six month and twelve months is defined as the time in months from the first dose of the drug to the date of death or the first documented date of progression, whichever comes first. For patients who did not die and did not have progression, the PFS is censored at the last documented tumor assessment. Survival curve for PFS will be generated using the Kaplan-Meier method. Median PFS with 95% CI will be computed. Those without an event are censored at their last valid tumor assessment, or at the last tumor assessment before patient start of the new therapy if a patient has started new anti-cancer therapy.

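### PFS and duration of response each have conflicting definitions, and the SAP's non-reporting clauses for OS and CFS can be read as dropping listed endpoints

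*SAP*

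**What the plan says.** **PFS.** Five places bear on what counts as progression:

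| Place | Rule |
|---|---|
| Protocol 2.2.2 (listed secondary endpoint) | "first progression to higher grade or stage, including muscle-invasive disease or death from any cause" |
| SAP 2.b.iv (listed secondary endpoint) | the same wording as protocol 2.2.2 |
| Protocol 8.2 (evaluation criteria) | "first evidence of muscle invasive bladder cancer, metastatic disease, or death due to any cause" |
| SAP 8.d (analysis) | "the date of death or the first documented date of progression, whichever comes first", with progression not defined there |
| Protocol 6.8 (prohibited treatments) | radiation or surgery involving tumor lesions is treated as disease progression on the date of the procedure |

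**Duration of response.** SAP 8.c uses "time from the date of first response (complete response (CR), partial response (PR), pathological complete response (pCR)) to the first date of non-response". SAP 5.c assigns all of Section 8 to the evaluable population, with no restriction to CIS. Protocol 8.2 covers only patients with CIS at entry who achieve a complete response (CR): "duration is defined as time from first documentation of CR to time of first high grade recurrence". Its censoring rule follows: "Patients who remain CR at end of study (EOS) are censored at their last cystoscopy date". The SAP places that same sentence in 8.b, under the CR rate, and 8.c has no censoring rule.

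**OS and CFS.** Protocol 10.2 plans Kaplan-Meier curves for both, without condition. SAP 8.e and 8.g also plan a curve and a median for each. Each item then ends with a clause: OS goes unreported if the absence of deaths means it cannot be calculated, and CFS goes unreported if too few cystectomies mean it cannot be calculated. No number of cystectomies is given. Both documents define CFS to include death as an event.

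**The concern.** PFS is a listed secondary endpoint, and the protocol gives it two different event sets. A move from Ta to T1 is an event under 2.2.2 and not under 8.2. Unless this is settled before analysis, the choice could be made with the data in view, in an open-label single-arm trial.

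The two versions of duration of response differ in population, qualifying response and end event. SAP 8.c cannot be programmed as it stands, because PR and pCR appear only as expanded abbreviations and non-response has no criteria. Grade matters here, since the plan foresees that "Low-grade recurrence will be tolerated without treatment interruption".

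For OS and CFS, whether a listed endpoint appears in the results may depend on how many events occur and, for CFS, on a threshold that nobody has stated.

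**Working it through.** **The plan's own precision figure.** Protocol 10.1 gives a Wilson lower limit of 37.6% for n = 18 and 60%. Check, with z² = 3.84:

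- Centre term: 0.60 + 3.84/36 = 0.707
- Half-width term: 1.96 × √(0.24/18 + 3.84/1296) = 0.250
- Divisor: 1 + 3.84/18 = 1.213
- Lower limit: (0.707 − 0.250)/1.213 = 37.6%, which reproduces.

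That figure concerns Month 6 completion and does not bear on this point. The plan gives no figure for PFS, duration, OS or CFS. The examples below take n = 18 from protocol 10.1 and assume complete follow-up to the landmark.

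**PFS.** Muscle invasion and metastasis are rises in stage, and death is in both lists, so every 8.2 event is also a 2.2.2 event. PFS under 2.2.2 therefore cannot exceed PFS under 8.2.

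- A patient whose only event by the landmark is a rise short of muscle invasion: 1/18 = 5.6 points lower under 2.2.2.
- A patient with such a rise who also has an 8.2 event by the landmark: no difference at that landmark.
- One to three patients of the first kind (assumed; the documents give no rate): 5.6 to 3/18 = 16.7 points.
- Example with one 8.2 event and two patients of the first kind: 17/18 = 94.4% (Wilson 74.2 to 99.0) under 8.2, and 15/18 = 83.3% (Wilson 60.8 to 94.2) under 2.2.2.

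**Duration.**

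| | SAP 8.c | Protocol 8.2 |
|---|---|---|
| Patients | evaluable responders | CIS patients with CR |
| Start | first CR, PR or pCR | first documented CR |
| End | first non-response (undefined) | first high-grade recurrence |
| Censoring | none stated in 8.c | last cystoscopy, if still CR at end of study |

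Take an assumed CIS patient with CR at month 3, low-grade recurrence at month 6 and high-grade recurrence at month 12. If low-grade recurrence is non-response, 8.c gives 6 − 3 = 3 months. Protocol 8.2 gives 12 − 3 = 9 months, provided the month-3 cystoscopy and cytology date the CR. If CR in CIS needs the 6-month biopsy, this patient may never enter the protocol analysis. The documents do not say which date applies.

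**OS with no deaths.** The Kaplan-Meier estimate is 100% and only the median is not estimable. Lower two-sided 95% limit: exact 0.025^(1/18) = 81.5%; Wilson 18/(18 + 3.84) = 82.4%. For an assumed death risk d over follow-up, the chance of no deaths is (1 − d)^18: 70% at d = 2%, 40% at 5%, 15% at 10% and 2% at 20%. The documents give no death rate.

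**CFS with no cystectomies.** The CFS events are then the deaths. With one to three deaths (assumed):

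- 17/18 = 94.4% (exact 95% CI 72.7 to 99.9)
- 16/18 = 88.9% (65.3 to 98.6)
- 15/18 = 83.3% (58.6 to 96.4)

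Few cystectomies therefore do not make CFS incalculable.

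**The case against.** The strongest reply is that these are descriptive secondary analyses in a small phase Ib trial, that the SAP can be read as defining progression once, in 2.b.iv, and that the protocol governs where the two documents differ. The descriptive status stands. The other two arguments do not settle PFS, because the protocol contradicts itself. SAP 8.d also carries the censoring rule of protocol 8.2, which points the analyst back to the narrower definition.

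On OS and CFS, a reader might infer that the SAP abandons these endpoints. The documents do not support that. Both items plan the curve, the clauses are conditional on the quantity not being calculable, and they directly follow the sentence on the median, so they may concern the median alone. Read literally, the CFS clause might never apply. What stands is the ambiguity: either clause can also be read as covering the whole endpoint.

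A reader might also infer that death during response is unaddressed. Protocol 8.2 does count death without recurrence as a high-grade recurrence, under time to high-grade recurrence. The rule is simply not repeated under duration.

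Finally, a reader might size the PFS gap from the progression rates in protocol 1.2. The Ta figure there is for patients without additional treatment, and the text gives neither a time frame nor the share short of muscle invasion, so those rates do not support a size.

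**Conclusion.** The point holds. PFS has two incompatible event sets, plus an unreconciled statement in protocol 6.8. The gap is 5.6 points for each patient whose only event by the landmark is a rise short of muscle invasion, with n = 18 and complete follow-up. It would be wrong to infer that every such rise costs 5.6 points: the effect is zero once that patient also has an 8.2 event by the landmark. How many patients will be affected is unknown.

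Duration of response differs in population, start and end event, and 8.c lacks the criteria needed to run it. It is not a listed endpoint, but protocol 10.2 and SAP 8.c both plan its curve.

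The OS and CFS clauses rest on an incorrect premise if they mean the whole endpoint, and are needed only as a note on the median if they do not.

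Two minor items belong with these. SAP 8.f and 8.g label the RFS and CFS medians as PFS. The SAP also omits the 6-month biopsy rule for CIS, and its exemption after re-induction, from its CR definition. The primary endpoint and sample size are unaffected.

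**What to change.** Before analysis:

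- **PFS.** Use the listed-endpoint definition (protocol 2.2.2, SAP 2.b.iv) in protocol 8.2 and SAP 8.d, and report the 8.2 definition as a sensitivity analysis. Reconcile the protocol 6.8 sentence by stating whether it defines a PFS event.
- **Duration.** Replace the SAP 8.c text with the protocol 8.2 definition, delete PR and pCR, and move the censoring sentence from 8.b to 8.c. State that the death convention given for time to high-grade recurrence applies. State whether first CR is dated at the month-3 cystoscopy and cytology or at the 6-month CIS biopsy. Match the term in protocol 10.2.
- **OS and CFS.** Delete both non-reporting clauses. Always give the curve, event counts and 6- and 12-month estimates with confidence intervals, and show the median as not reached where that applies.
- **Minor.** Name the medians in SAP 8.f and 8.g as RFS and CFS. Carry the protocol 8.2 CIS biopsy rule and its re-induction exemption into the SAP definition of CR.

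The cost is wording in two documents and one extra PFS row, with no added patients, visits or biopsies. The drawback is that duration rests on the CIS subset alone, whose size the documents do not give, so its interval will be wide. Responders without CIS are still described by RFS in SAP 8.f.

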6.7 Treatment Discontinuation

Patients must permanently discontinue study treatment (avelumab and BCG) if they experience any of the following:

- Intolerable toxicity related to study treatment, including development of an immune mediated adverse event determined by the investigator to be unacceptable given the individual patient's potential response to therapy and severity of the event
- Any medical condition that may jeopardize the patient's safety if he or she continues study treatment
- Investigator determines it is in the best interest of the patient
- Use of another non-protocol anti-cancer therapy
- Pregnancy
- Loss of clinical benefit as determined by the investigator after an integrated assessment of cystoscopy, radiographic and local biopsy results (if available), and clinical status (e.g., symptomatic deterioration such as pain secondary to disease)
- Patients have Cystoscopy or Radiographic disease progression or symptomatic deterioration attributed to disease progression

The primary reason for study treatment discontinuation should be documented in the patient's medical records. Patients who discontinue study treatment prematurely will be replaced.

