6.9 Duration of Follow-up

The maximum follow-up period will be up to 1 year. For this protocol, all patients, including those who discontinue protocol therapy early, will be followed for response until progression or to the date of censoring (dropout, end of study), and for survival every three months. All patients must also be followed through completion of all protocol therapy. See Section 7.2.2 for additional details.

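### PFS is cut back to before new anti-cancer therapy only for patients who never have an event, so censoring depends on the later outcome and the Kaplan-Meier curve is biased downward

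*SAP*

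**What the plan says.** SAP 8.d (Antitumor Evaluation) runs PFS from first dose "to the date of death or the first documented date of progression, whichever comes first". It sets no limit on events that follow new therapy. Two censoring sentences come after this:

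- The first makes no mention of new therapy: "For patients who did not die and did not have progression, the PFS is censored at the last documented tumor assessment".
- The second adds a cut for patients who started new anti-cancer therapy. Patients without an event "are censored at their last valid tumor assessment, or at the last tumor assessment before patient start of the new therapy".

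Protocol 8.2 has only the second form, with the same restriction: "Those without an event are censored at their last valid tumor assessment", or at the last assessment before new therapy.

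Four other places bear on whether the rule will be used:

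- Protocol 2.2.2: "Patients with persistent or recurrent high-grade disease at 6 Month cystoscopy will be taken off treatment".
- Protocol 6.7 lists "Use of another non-protocol anti-cancer therapy" as a reason to stop study treatment. Neither PFS definition makes it an event.
- Protocol 6.9: "all patients, including those who discontinue protocol therapy early, will be followed for response until progression or to the date of censoring". The censoring reasons given there in brackets are dropout and end of study, not new therapy.
- Protocol 7.2.2 continues three-monthly cystoscopy and cytology for one year, or until progression, in patients who stopped treatment for reasons other than progression.

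**The concern.** Take two patients who come off treatment at Month 6 without a PFS event and start new therapy at Month 7. One progresses at Month 12, the other is still progression-free at Month 18. As written, the first stays at risk and is an event at Month 12. The second is moved back and censored at Month 6. Their status at the switch was identical, and only the later outcome separates them.

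Kaplan-Meier requires that censoring at a given time not depend on what happens afterwards. This rule breaks that requirement in a known direction: failures after the switch are kept and successes are removed from the risk set. Follow-up continues off treatment, so such events can be recorded. PFS at 12 months, a named secondary endpoint, and the median PFS would both be affected.

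**Working it through.** The documents give no PFS rate, event count or switching rate, so there is no PFS figure of theirs to reproduce.

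**Three rules compared**

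- All follow-up: every event counts, and event-free patients are censored at the last assessment.
- As written: every event counts, and event-free switchers are censored before new therapy.
- Uniform cut: every switcher is censored before new therapy, and later events are not counted.

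**Direction.** The first two rules have the same events at the same times. The as-written rule only removes event-free patients from risk sets, so each factor (1 − d/n) is equal or smaller. Its curve can never lie above the all-follow-up curve, whatever the assumptions.

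**Small example (hypothetical, 18 patients).** Twelve have no new therapy: 3 events at Month 6, 9 event-free. Six start new therapy at Month 4 (last prior assessment Month 3): 3 progress at Month 9, 3 stay event-free. PFS at 12 months:

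- All follow-up: (15/18) × (12/15) = 66.7%
- As written: (12/15) × (9/12) = 60.0%
- Uniform cut: 9/12 = 75.0%

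**Size.** All inputs here are assumptions: a fraction p switches at Month 6 progression-free, yearly risk after switching is r, yearly risk in the others is 10%, and switchers are followed to Month 18. Take p = 0.40 and r = 0.35.

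- PFS at Month 6: 0.60 × 0.9^0.5 + 0.40 = 0.5692 + 0.40 = 0.9692. It is the same under all three rules, because all switching is placed at Month 6.
- All follow-up, Month 12: 0.60 × 0.9 + 0.40 × 0.65^0.5 = 0.5400 + 0.3225 = **86.2%**.
- As written: just after Month 6 the only switchers left at risk are those who will have an event by Month 18, that is 0.40 × 0.35 = 0.1400. The risk set is 0.5692 + 0.1400 = 0.7092. At Month 12, 0.5400 + 0.40 × (0.8062 − 0.65) = 0.6025 remains. PFS = 0.9692 × 0.6025/0.7092 = **82.3%**.
- Uniform cut: 0.9692 × 0.9^0.5 = **91.9%**.

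The same formulas for other inputs give the shortfall of the as-written rule at Month 12, in percentage points:

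| Switching p | r = 20% | r = 35% | r = 50% |
|---|---|---|---|
| 5% | 0.2 | 0.2 | 0.2 |
| 10% | 0.5 | 0.5 | 0.4 |
| 20% | 1.2 | 1.2 | 1.1 |
| 40% | 3.5 | 3.9 | 3.8 |

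The switching rate drives the result; the risk after switching hardly matters.

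**Against sampling error.** With 18 patients and PFS of 86.2%, the binomial standard error is √(0.862 × 0.138/18) = 8.1 points.

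**Heavier switching.** A simulation let new therapy start any time after Month 3, independently of event risk, with 20 to 60% starting by Month 12 and true 12-month PFS of 50 to 80%. The shortfall was at most 1.3 points at Month 6 and 1.6 to 7.4 points at Month 12. The standard deviation across trials of 18 was about 12 to 14 points at Month 12 when the true value was 60% and 40% started new therapy. Nothing in the documents supports switching rates that high.

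**The case against.** **The two SAP sentences need not conflict.** A reader might infer that SAP 8.d holds two competing rules. The second sentence covers the first and adds a special case, and Protocol 8.2 has only the fuller form. General rule plus refinement is the natural reading. This stands: the duplication is untidy but secondary. It does not remove the outcome-dependent cut, which is in both documents.

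**Switchers may be few.** It is tempting to take 40% from the plan's expected 60% completion of Month 6 maintenance and call switching common. The documents do not support that. Non-completion also covers toxicity, missed or late instillations, withdrawal, and progression that is already a PFS event. Nothing says that non-completers start new therapy while progression-free, so 40% is close to a ceiling.

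**Some later treatments are already events.** Protocol 6.8 counts radiation, or surgery involving tumor lesions, as progression when performed. Where that applies, the new-therapy cut never operates. The note sits in a list for the screening and treatment phase and is not repeated in Protocol 8.2 or SAP 8.d, so its reach after discontinuation is unclear. It does not cover drug or intravesical therapy. It narrows the problem without closing it.

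**Larger gaps lie beyond the named landmarks.** At Month 18 the 40%/35% scenario gives 77.2% with all follow-up and 70.0% as written. PFS is named only at 6 and 12 months, so this is not the size of the problem, although the planned curve may extend that far.

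**A uniform cut was surely meant.** Possibly, but the text restricts the cut to patients without an event. A uniform cut would give a third answer, about 10 points above the as-written rule at Month 12 in the 40%/35% scenario.

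**Conclusion.** The rule is wrong as written, and the direction of the bias is certain: PFS is never overstated and generally understated relative to all follow-up. Only the size rests on assumptions. With switching placed at Month 6, the effect is nil at that landmark. At Month 12 it runs from under 1 point (5 to 10% switching) to about 4 points (40%). Any of these is smaller than the sampling error with 18 patients. PFS is secondary, with no test or decision rule attached, so the primary endpoint and the sample size are untouched. The case for changing it is that the error is systematic, the handling of events after new therapy is better settled before the data are seen, and the correction costs almost nothing. Choosing between no cut and a uniform cut is a choice of estimand; making the cut depend on the later outcome is not defensible under either.

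**What to change.** In SAP 8.d and Protocol 8.2, state one rule that applies to every patient whatever happens later. Preferred main analysis: count progression or death whenever it occurs, censor event-free patients at the last valid tumor assessment regardless of new therapy, and delete the duplicate SAP sentence. Add one sensitivity analysis that censors all switchers, with or without a later event, at the last assessment before new therapy. Note beside it that this cut is itself informative if patients switch because of persistent or recurrent disease, which is why the no-cut rule is the safer main analysis. State also whether the Protocol 6.8 note on radiation and surgery applies to PFS after treatment has stopped.

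The cost is a sentence or two in each document and one extra curve. The downside is that the main PFS then includes the effect of later therapy.
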